Amendment 1	18 June 2019	
 Increased the number of participants to up to 650 throughout, as up to 150 participants will be randomized in the southern hemisphere. Expanded the gestational age of maternal participants to between ≥ 24 0/7 and ≤ 36 0/7 weeks at the time of vaccination. Added a statement that enrollment will be monitored to help ensure distribution of maternal participants across the gestational age range. Removed the 1-week follow-up visit for maternal participants and updated associated study endpoints, stopping rule, procedures, and assessments throughout, as appropriate, in order to reduce the burden on maternal participants. Removed the 1-month postdelivery and 12-month postdelivery blood draws for serologic assessment for maternal participants and updated associated study endpoints in order to reduce the burden on maternal participants. Removed the calculation of body mass index (BMI), as height and weight will be entered in the case report form (CRF). Updated the route of the temperatures taken for infant participants to rectal throughout, as appropriate, as requested by the Center for Biologics Evaluation and Research (CBER). Removed the 12-month postdelivery visit blood draws for serologic assessment for infant participants and updated associated study objectives and endpoints and procedures, as appropriate, in order to reduce the burden on infant participants. 

Document History		
Document	Version Date	Summary of Changes and Rationale
		
CCI
 
[REDACTED]
 
CCI
 
 Removed reference to RSV vaccine study arms' being dropped in Section 4.1, as no vaccine study arms will be dropped. Added a statement to Section 4.1 that the study will be conducted in more than 1 geographic location. Clarified that calculation of gestational age must be based upon ultrasound results obtained at ≥ 18 weeks of pregnancy in Section 5.1.1, as requested by CBER. Clarified that if an ultrasound examination is not performed at ≥ 18 weeks of pregnancy as standard of care, then an ultrasound examination must be performed and reviewed as part of the screening visit in the schedule of activities, Section 5.1.1, and Section 8.10.1.1. Added clarification that the stopper on the water-for-injection vial may contain latex. Added clarification that exclusion criterion 7 applies to current and previous pregnancies. Updated text to align time periods for recording concomitant medications with those for reporting adverse events (AEs) for maternal and infant participants in Section 6.5.3, Section 6.5.5, and throughout, as required. 
CCI
 
[REDACTED]
 
 Clarified that the back and genitourinary body systems must be assessed as part of the infant physical examination in Section 8.10.2 and throughout, as required. Reduced the total volume of blood collected for both maternal and infant participants in Section 8.2.13. 
CCI
 
[REDACTED]

Document History		
Document	Version Date	Summary of Changes and Rationale
		
CCI CCI
 
[REDACTED]
 
 Added subgroup analyses of the secondary immunogenicity endpoints, including an analysis based on gestational-age subcategories in Section 9.4.1.1, as requested by CBER. In Section 9.5.1, clarified that additional analyses may be performed at any time during the study and that they may be based on fewer than the total planned number of participants in order to allow earlier analysis of data. Added the definition of a medically attended adverse event to Section 10.3.
Original protocol	11 March 2019	N/A

This amendment incorporates all revisions to date, including amendments made at the request of country health authorities and institutional review boards (IRBs)/ethics committees (ECs).

TABLE OF CONTENTS

LIST OF TABLES	10
1. PROTOCOL SUMMARY	12
1.1. Synopsis	12
1.2. Schema	13
1.3. Schedule of Activities (SoA).....	14

1. PROTOCOL SUMMARY

1.1. Synopsis

This is a Phase 2b, multicenter, randomized, placebo-controlled study in which up to 650 healthy pregnant women 18 through 49 years of age will be randomized to receive one of 2 dose levels of bivalent (respiratory syncytial virus [RSV] A and B) respiratory syncytial virus stabilized prefusion F subunit vaccine (RSV vaccine) at 120 µg (60 µg A and 60 µg B) and 240 µg (120 µg A and 120 µg B) of the prefusion RSV F antigen, formulated with or without aluminum hydroxide (Al(OH)₃), or placebo (1:1:1:1:1 randomization). Assessments will include descriptions of safety, tolerability, and immunogenicity in maternal participants as well as safety and characteristics of transplacentally transferred antibodies in their infants.

CCI

This study will use stopping rules. An internal review committee (IRC) and an external data monitoring committee (E-DMC) will monitor safety in this study.

Approximate Duration of Participant Participation

Pregnant women will participate in the study from enrollment during their pregnancy, and for approximately 12 months after delivery of their newborn infants.

Pregnant women will be vaccinated at a time of year such that the infant is likely to be exposed to RSV during the first 6 months of life.

Infants will participate from birth to approximately 12 months of age.

Approximate Number of Participants

Up to 650 healthy pregnant women will be randomized. Enrollment will be monitored to help ensure distribution of vaccination across the gestational age range of ≥ 24 0/7 and ≤ 36 0/7 weeks.

Respiratory Syncytial Virus Stabilized Prefusion F Subunit Vaccine

- The active ingredients in the RSV vaccine are 2 stabilized prefusion RSV F antigens, in equal amounts from virus subgroups A and B, in a lyophilized dosage form for reconstitution. The vaccine is supplied as a lyophilized cake that is reconstituted by diluent with either sterile water for injection or a sterile suspension of Al(OH)₃ in water for injection.

Placebo

- The placebo for RSV vaccine will be a sterile normal saline solution for injection (0.9% sodium chloride injection, in a 0.5-mL dose).

Data Monitoring Committee

This study will use an IRC and an E-DMC.

Statistical Methods

There is no statistical hypothesis specified in this study. The primary objectives are to describe the safety and tolerability of 2 dose levels of RSV vaccine candidate with or without Al(OH)₃ in maternal participants and to assess the safety of maternal immunization in infant participants born to women 18 through 49 years of age who were vaccinated with 1 dose of RSV vaccine during pregnancy. The safety populations will be used to evaluate the primary objectives.

Safety data will be analyzed separately for maternal participants and infant participants. Maternal participants will be analyzed according to the investigational product received, and infant participants will be analyzed according to the investigational product their mothers (maternal participants) received.

Immunogenicity data for maternal participants and infant participants will be summarized separately with the exception of maternal-to-infant placental transfer analysis. Participants will be summarized according to the vaccine group to which they (for maternal participants) or their mothers (for infant participants) were randomized.

All safety and immunogenicity analyses will be descriptive in nature.

An analysis will be performed when the delivery-visit RSV-neutralizing antibody titer data from all maternal and infant participants and the 1-month-after-birth visit data for infant participants are available. A further analysis will be performed when all data are available from the infant participants' 6-month visit. Additional analyses may be conducted before the final analysis to support internal program-level decisions as needed.

The final analysis will be performed after all participants have completed the study and when all of the data are available.

1.2. Schema

Not applicable.

1.3. Schedule of Activities (SoA)

The SoA tables provide an overview of the protocol visits and procedures. Refer to the [Study Assessments and Procedures](#) section of the protocol for detailed information on each procedure and assessment required for compliance with the protocol.

The investigator may schedule visits (unplanned visits) in addition to those listed in the SoA table, in order to conduct evaluations or assessments required to protect the well-being of the participant.

1.3.1. Schedule of Activities for Maternal Participants

Visit Description	Screening (Visit 0)	Vaccination	2-Week Follow-up Visit	1-Month Follow-up Visit	Delivery	1-Month Postdelivery Visit	6-Month Postdelivery Visit	12-Month Postdelivery Visit
Visit Window (Days)	Day -14 to Day -2 Prior to Vaccination ^a	Day 1	14 to 17 Days After Vaccination ^b	28 to 42 Days After Vaccination ^b	Varies	28 to 35 Days After Delivery	168 to 210 Days After Delivery	350 to 378 Days After Delivery
Informed consent	X							
Assign single maternal participant identifier	X							
Demography	X							
Record current alcohol, tobacco, and marijuana usage	X							
Medical history including obstetric history ^c	X							
Record LMP and EDD	X							
Vital signs ^d	X	X	X	X				
Physical examination	X							
Measure weight and height	X							
Measure weight		X	X	X				
Obstetric examination	X	X	X	X				
Record baseline concomitant medication	X							
Record details of any antenatal steroid treatment, monoclonal antibodies, blood transfusions, or Rho(D) immune globulin	X	X	X	X	X	X	X	X
Record nonstudy vaccine information	X	X	X	X	X	X	X	X
Review eligibility criteria	X							
Blood draw for hematology and blood chemistry assessments	X							
Review laboratory results for hematology and chemistry assessments ^e		X						
Blood draw for HBV, HCV, HIV, and syphilis testing	X							
Review results from HBV, HCV, HIV, and syphilis testing ^e		X						
Review temporary delay criteria		X						
Review continued eligibility		X	X	X	X			
Blood draw for serologic assessment (~25 mL per blood sample)		X	X	X	X		X	

Visit Description	Screening (Visit 0)	Vaccination	2-Week Follow-up Visit	1-Month Follow-up Visit	Delivery	1-Month Postdelivery Visit	6-Month Postdelivery Visit	12-Month Postdelivery Visit
Visit Window (Days)	Day -14 to Day -2 Prior to Vaccination ^a	Day 1	14 to 17 Days After Vaccination ^b	28 to 42 Days After Vaccination ^b	Varies	28 to 35 Days After Delivery	168 to 210 Days After Delivery	350 to 378 Days After Delivery
Urine sample for glucose and protein testing	X	X						
Assign randomization and container number		X						
Administer investigational product		X						
Postvaccination observation ^f and assessment of immediate adverse events		X						
Dispense e-diary, digital thermometer, and measuring device ^g		X						
Review and/or collect e-diary ^h			X					
Record pregnancy outcome information					X			
Record concomitant medication taken to treat an adverse event		X	X	X	X	X	X	X
Record adverse events, medically attended adverse events, and serious adverse events, as appropriate ⁱ	X	X	X	X	X	X	X	X
Surveillance reminder contact					Contact the maternal participant approximately every week until approximately 6 months after delivery			

Abbreviations: EDD = estimated delivery date; e-diary = electronic diary; HBV = hepatitis B virus; HCV = hepatitis C virus; HIV = human immunodeficiency virus; LMP = last menstrual period.

Visit Description	Screening (Visit 0)	Vaccination	2-Week Follow-up Visit	1-Month Follow-up Visit	Delivery	1-Month Postdelivery Visit	6-Month Postdelivery Visit	12-Month Postdelivery Visit
Visit Window (Days)	Day -14 to Day -2 Prior to Vaccination ^a	Day 1	14 to 17 Days After Vaccination ^b	28 to 42 Days After Vaccination ^b	Varies	28 to 35 Days After Delivery	168 to 210 Days After Delivery	350 to 378 Days After Delivery

- a. Screening may take place on Day -1 (1 day prior to vaccination) if all laboratory results are available for review prior to vaccination.
- b. The 2-week follow-up and 1-month follow-up visits will not be performed if delivery occurs before the visits. Once delivery occurs, the visit windows are calculated based on the delivery date.
- c. Where an obstetric ultrasound examination is not performed at ≥ 18 weeks of pregnancy as part of prenatal standard of care, perform an ultrasound examination and record findings.
- d. Vital signs include oral temperature, seated blood pressure, and heart rate.
- e. Laboratory results should be reviewed as soon as they are available.
- f. The first 5 maternal participants in the study will be observed for at least 4 hours after investigational product administration. Further vaccination will commence no sooner than 48 hours after the fifth maternal participant received her vaccination. All other maternal participants will be observed for at least 30 minutes.
- g. Maternal participants will record (in an e-diary) reactogenicity events each evening for 7 days following vaccination. Remind maternal participants that study staff may contact them to obtain additional information on events entered into the e-diary. Ask maternal participants to contact the investigator or site staff immediately if they are prompted by the e-diary from Day 1 to Day 7 following vaccination to determine if an unscheduled visit is required.
- h. Designated site staff will review e-diary data online at frequent intervals for the 7 days following vaccination to evaluate maternal participant compliance and as part of the ongoing safety review.
- i. The investigator and site staff will ensure the active elicitation and collection of AEs and SAEs through 1 month after vaccination. From 1 month after vaccination until the maternal participant completes the study, MAEs and SAEs will be collected.

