4.1.2. Approximate Number of Participants

Up to 650 healthy pregnant women will be randomized. Approximately 500 women will be randomized in the northern hemisphere and up to 150 additional women will be randomized in the southern hemisphere. Enrollment will be monitored to help ensure distribution of vaccination across the gestational age range of ≥ 24 0/7 and ≤ 36 0/7 weeks.

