5.1.1. Inclusion Criteria – Maternal Participants

Age and Sex:

1. Healthy women ≥ 18 and ≤ 49 years of age who are between 24 0/7 and 36 0/7 weeks of gestation on the day of planned vaccination, with an uncomplicated, singleton pregnancy, who are at no known increased risk for complications, and whose fetus has no significant abnormalities observed on ultrasound.

Note: Gestational age must be based upon ultrasound results obtained at ≥ 18 weeks of pregnancy.

Type of Participant and Disease Characteristics:

2. Willing and able to comply with scheduled visits, treatment plan, laboratory tests, and other study procedures.
3. Receiving prenatal standard of care.
4. Had an ultrasound performed at ≥ 18 weeks of pregnancy.

Note: Where an obstetric ultrasound is not performed at ≥ 18 weeks of pregnancy as part of prenatal standard of care, an ultrasound must be performed and reviewed as part of the screening visit.

5. Had a negative urinalysis for protein and glucose at the screening visit (Visit 0). Trace protein in the urine is acceptable if the blood pressure is also normal.
6. Determined by medical history, physical examination, screening laboratory assessment, and clinical judgment to be appropriate for inclusion in the study.

7. Expected to be available for the duration of the study, can be contacted by telephone during study participation, and is willing to give informed consent for her infant to participate in the study.
8. Documented negative human immunodeficiency virus (HIV) antibody, hepatitis B virus (HBV) surface antigen, hepatitis C virus (HCV) antibody, and syphilis tests at the screening visit (Visit 0).

Weight:

9. Body mass index (BMI) of $<40 \text{ kg/m}^2$ at the time of the screening visit.

Informed Consent:

10. Capable of giving signed informed consent as described in [Appendix 1](#), which includes compliance with the requirements and restrictions listed in the informed consent document (ICD) and in this protocol.

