8.10.1.3. Maternal Participants: 2-Week Follow-up Visit (14 to 17 Days After Vaccination)

If delivery occurs before this visit, this visit will not be conducted.

- Ensure that the maternal participant continues to be eligible for the study and meets none of the maternal participant withdrawal criteria as described in [Section 7.2](#).
- Measure vital signs, including oral temperature, seated blood pressure, and heart rate.
- Measure and record weight.
- Perform obstetric examination including but not limited to fundal height, fetal heart tones, and fetal movement.
- Collect a blood sample of approximately 25 mL for serologic assessments.
- Review the maternal participant's e-diary data and collect the e-diary (if applicable). Collect stop dates of any e-diary events ongoing on the last day that the e-diary was completed and record stop dates in the CRF.

- Record details of any antenatal steroid treatment, monoclonal antibodies, blood transfusions (eg, whole blood, packed cells), or Rho(D) immune globulin (eg, RhoGam) given since the last visit.
- Record any medication taken to treat an AE since the last visit.
- Record details of any nonstudy vaccinations given since the last visit.
- Ask the maternal participant to contact the site staff or investigator if a medically attended event (eg, doctor's visit, emergency room visit) or hospitalization occurs.
- Record AEs as described in [Section 8.3](#) and [Section 10.3.3](#).
- Complete the participant's source documents.
- The investigator or an authorized designee completes the CRF.

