8.10.1.4. Maternal Participants: 1-Month Follow-up Visit (28 to 42 Days After Vaccination)

If delivery occurs before this visit, this visit will not be conducted.

- Ensure that the maternal participant continues to be eligible for the study and meets none of the participant withdrawal criteria as described in [Section 7.2](#).
- Measure vital signs, including oral temperature, seated blood pressure, and heart rate.
- Measure and record weight.
- Perform obstetric examination including but not limited to fundal height, fetal heart tones, and fetal movement.
- Collect a blood sample of approximately 25 mL for serologic assessments.
- Record details of any antenatal steroid treatment, monoclonal antibodies, blood transfusions (eg, whole blood, packed cells), or Rho(D) immune globulin (eg, RhoGam) given since the last visit.
- Record any medication taken to treat an AE since the last visit.
- Record details of any nonstudy vaccinations given since the last visit.
- Complete the maternal participant's source documents.
- Ask the maternal participant to contact the site staff or investigator if a medically attended event (eg, doctor's visit, emergency room visit) or hospitalization occurs.

- Record AEs as described in [Section 8.3](#) and [Section 10.3.3](#).
- The investigator or an authorized designee completes the CRF.

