9.1.1. Estimands – Maternal Participants

9.1.1.1. Safety:

In maternal participants receiving 1 dose of investigational product:

- The percentage of maternal participants reporting local reactions
- The percentage of maternal participants reporting systemic events
- The percentage of maternal participants reporting AEs

- The percentage of maternal participants reporting obstetric complications, MAEs, and SAEs

Missing e-diary data will not be imputed; missing AE dates and missing AE intensity will be handled according to Pfizer safety rules.

9.1.1.2. Immunogenicity:

In maternal participants receiving 1 dose of investigational product and in compliance with the key protocol criteria (evaluable participants):

- The immune response, estimated by the GMT for RSV A– and RSV B–neutralizing antibody titers
- The immune response, estimated by the GMFR from baseline in RSV A– and RSV B–neutralizing antibody titers
- GMR, estimated by the ratio of the GMTs for RSV A– and RSV B–neutralizing antibody titers of the RSV vaccine group and the placebo group

These estimands estimate the vaccine effect in the hypothetical setting where participants follow the study schedules and protocol requirements as directed. Missing serology results will not be imputed, as missing completely at random (MCAR) is assumed. For participants who discontinue from the study or have major protocol violations, all postdiscontinuation or violation observations will be censored.

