1. VERSION HISTORY

Table 1. Summary of Changes

Version/ Date	Associated Protocol Amendment	Rationale	Specific Changes
1/ 13 Aug 2019	Amendment 1/ 18 Jun 2019	N/A	N/A
2 (Amendment 1)/ 18 Nov 2019	Amendment 1/ 18 Jun 2019	
 Updated description of evaluable maternal population as not all maternal subjects will have a 1 month postvaccination visit. Removed a planned analysis and a subset analysis Added details for clarity 	
 Updated the author’s job title Updated the evaluable maternal population (in Section 4) to remove reference to “1 month after vaccination” for the blood draw and to specify time frame of assay results. Updated the evaluable infant population (in Section 4) to make it more time point-specific Updated Section 6.4 (Table 8 and Table 9) to remove the reference to subset analysis for GA subgroup “27 to <33 weeks” Updated Section 7.2 with new information regarding available assay data and added text regarding “preliminary evaluable populations” Updated Section 7.2 to remove reference to a planned analysis on 500 US participants

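### Maternal titers are assumed missing completely at random, but the plan cancels the 1-month draw once a woman delivers, so missingness depends on gestational age at vaccination

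*Protocol*

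**What the plan says.** On missing data, Protocol 9.1.1.2 states: "Missing serology results will not be imputed, as missing completely at random (MCAR) is assumed". SAP 2.1.5.1 repeats this for all three maternal estimands: geometric mean titer (GMT), geometric mean fold rise (GMFR) and vaccine-to-placebo geometric mean ratio (GMR).

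On visits, footnote b of the maternal schedule (Protocol 1.3.1) says: "The 2-week follow-up and 1-month follow-up visits will not be performed if delivery occurs before the visits". The 1-month procedures (Protocol 8.10.1.4) repeat it: "If delivery occurs before this visit, this visit will not be conducted". The 2-week procedures (8.10.1.3) carry the same rule. The windows are days 14-17 and days 28-42 after vaccination.

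On who is vaccinated, Protocol 5.1.1 admits women "between 24 0/7 and 36 0/7 weeks of gestation on the day of planned vaccination", and Protocol 4.1.2 adds: "Enrollment will be monitored to help ensure distribution of vaccination across the gestational age range".

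The SAP recognizes the consequence. Its version history gives as a reason for revising the evaluable maternal population that "not all maternal subjects will have a 1 month postvaccination visit". The MCAR statement stayed. The intercurrent events listed in SAP 2.1.5.1 and 6.2.1.1.1 are discontinuation and protocol violation; delivery before the visit is not named.

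**The concern.** MCAR means that the chance of a missing result is unrelated to anything about the woman. Here it is tied by rule to the time left before delivery, and so to gestational age at vaccination.

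The evaluable maternal population needs only one valid result after vaccination (SAP 4). A woman without a 1-month sample can therefore still contribute at 2 weeks and at delivery. The GMTs at the three time points then rest on different sets of women, and the 1-month set leans toward earlier vaccination. If titers vary with gestational age, the overall 1-month GMT and GMFR, and any reading of change over time, mix that shift with the immune response.

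The 1-month titer has a prominent use. It is the outcome in the dose-by-formulation ANOVA (SAP 6.2.1.1.2) and in the maternal bar graphs (SAP 6.2.1.1.1), in a study that SAP 2 says will supply the data for choosing dose and formulation.

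**Working it through.** The documents give no expected share of missing maternal titers, so there is no planned figure to reproduce.

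**From the windows alone.** For the earliest 1-month draw (day 28), a woman vaccinated at 24 0/7 must still be pregnant at 28 0/7; one vaccinated at 36 0/7 must still be pregnant at 40 0/7. The loss cannot be equal across that range.

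**Inputs for the size.**
- Gestational age at vaccination, 24-36 weeks (Protocol 5.1.1). Assumed uniform, in line with the monitored spread in 4.1.2.
- Visit days 14, 17, 28, 35 and 42, from the windows in Protocol 8.10.1.3 and 8.10.1.4.
- Gestational age at delivery: not in the documents. Assumed normal, mean 39.0 or 39.5 weeks, SD 1.3 or 1.7 weeks.
- Group size: 650 / 5 = 130 (Protocol 9.2).

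**Formula.** With F the distribution of gestational age at delivery, a woman vaccinated at g weeks loses a draw due on day d with probability [F(g + d/7) - F(g)] / [1 - F(g)]. Example with mean 39.0, SD 1.7, g = 36, d = 28: (0.7218 - 0.0388) / (1 - 0.0388) = 0.71. At g = 30 the same formula gives 0.002.

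**Percent of draws lost**, averaged over g; range over the four mean/SD pairs:

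| Visit day | All | <30 wk | 30-<33 wk | ≥33 wk |
|---|---|---|---|---|
| 14 | 0.7-2.3 | 0.0 | 0.0-0.2 | 2.6-8.8 |
| 17 | 1.2-3.4 | 0.0 | 0.0-0.4 | 4.9-13.3 |
| 28 | 6.7-10.7 | 0.0 | 0.5-3.3 | 26.4-39.4 |
| 35 | 13.2-17.5 | 0.0-0.1 | 2.7-9.6 | 49.9-62.3 |
| 42 | 21.0-25.2 | 0.0-0.4 | 10.2-21.7 | 69.8-82.9 |

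MCAR would need the last three columns to be equal. Each row supposes that every visit falls on that day; actual visits will spread over the window.

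**In women per group.** Overall losses of 6.7-10.7%, 13.2-17.5% and 21.0-25.2% of 130 are about 9-14, 17-23 and 27-33. The band from 33 weeks holds 130 × 3/12 = 32.5; about 20-24 remain with a day-28 visit, 12-16 with day 35 and 6-10 with day 42.

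**Wider delivery range** (mean 38.8-39.6, SD 1.2-2.0): overall loss is 6-13% at day 28 and 20-27% at day 42; from 33 weeks it is 24-44% at day 28.

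**Shift in who is described.** Mean gestational age at vaccination is 30.0 weeks in all women. Among those with a sample it is 29.4-29.6 (day 28), 29.1-29.3 (day 35) and 28.6-28.9 (day 42).

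**What that could do to a GMT.** The documents give no relation between titer and gestational age. As illustration only, if titers rose by a fraction s per week, the 1-month GMT would be multiplied by (1 + s) raised to the shift. At day 28 with a shift of -0.56: 1.05^-0.56 = 0.97 and 1.10^-0.56 = 0.95. At day 42 with a shift of -1.41: 0.93 and 0.87. A falling relation would reverse the direction.

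**The case against.** **It is largely a labelling matter.** The estimand concerns participants who follow the schedule. A woman who delivers first has followed it, and no draw is due. The observed 1-month GMT is then a sound estimate for women still undelivered at the visit. This reading is defensible, but the plan does not state it, and it would rest on that definition rather than on MCAR.

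**It is partly handled.** SAP 6.4 plans maternal titers in four bands of gestational age at vaccination, and SAP 6.5.2 tabulates draws in and out of window by group. These displays show part of the problem. They do not correct the overall estimate, and the conditional mITT rerun cannot recover samples never taken.

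**It may be small beside sampling error.** If the SD of log titer is 0.7-1.0 (an assumption) and 105-120 women contribute per arm, the 95% CI half-width is about 13-21%. That exceeds the illustrated day-28 shift of 3-5%. This stands, although the day-42 shift of 7-13% is no longer clearly smaller, and titers are secondary in a study without hypothesis tests.

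**Stronger readings that do not hold.**
- A reader might infer that the GMRs or the dose-by-formulation comparison are biased. The rule is identical in every arm, so under randomization it does not do that by itself. It would take a vaccine effect on delivery timing. If the vaccine effect varies with gestational age, the GMR describes an earlier-vaccinated population.
- A reader might infer that every maternal titer is affected. Baseline is not, a delivery sample is planned (Protocol 8.10.1.5), and 2-week loss is about 1-2% at the start of its window.
- A reader might infer that few women vaccinated at 33 weeks or later keep a 1-month sample. With a day-28 visit, 61-74% keep it; a minority arises only from about day 35.

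**Conclusion.** The MCAR statement is wrong as written for the draws that delivery cancels. The contradiction follows from the documents alone; its size rests on the assumed delivery distribution, the uniform spread of vaccination and the visit day.

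The problem matters at 1 month, where nearly all the loss falls on women vaccinated at 30 weeks or later and most of it on those from 33 weeks. The t-based GMT, GMFR and GMR (SAP 5.2.2) and the 1-month ANOVA have no gestational-age term, so nothing planned corrects the overall values. The exposed quantities are the overall 1-month GMT and GMFR and their comparison with the 2-week and delivery values. How far those are off cannot be known without the titer-gestational-age relation. This is a correction worth making before unblinded analysis, not a threat to the randomized comparisons.

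**What to change.** 1. In Protocol 9.1.1.2 and SAP 2.1.5.1, replace MCAR with missing at random given gestational age at vaccination and baseline titer.
2. Name delivery before the visit as an intercurrent event, and state whether the 1-month estimate describes women still undelivered or all evaluable women.
3. In SAP 6.2.1.1.2, add gestational age at vaccination and baseline log titer to the 1-month ANOVA.
4. Report 1-month GMTs, GMFRs and GMRs standardized to the randomized gestational-age distribution, letting the gestational-age effect differ by arm, beside the observed-data values. This is preferable to one repeated-measures model across 2 weeks, 1 month and delivery with a common slope, because delivery is not a fixed time after vaccination.
5. In SAP 6.5.2, tabulate cancelled draws by arm and by the gestational-age bands of SAP Table 8.

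The cost is SAP text, a matching protocol sentence and a few outputs. The covariates are already collected, and no visit or sample changes. The downside is small: the standardized results are model-based, and the few samples from women vaccinated at 33 weeks or later carry extra weight and widen the intervals.
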